2. Verify Inclusion/Exclusion Criteria. Subjects will meet all the inclusion and none of the exclusion criteria.
3. Obtain demographics (race, ethnicity, sex, date of birth)
4. Obtain medical, medication, and headache history. Data collected will include medical history and diagnoses, age at onset of migraine and other pertinent migraine/headache history, history of acute and prophylactic headache medications within the past 30 days, and history of other recent/concomitant medications.
5. Obtain date of last menstrual cycle and perform urine pregnancy test, if appropriate. Results of the pregnancy test must be negative to continue in study.
6. Perform physical and neurological examinations.
7. Measure vital signs (height, weight, resting heart rate, and blood pressure).
8. Review Baseline Headache Diary. Subjects will be instructed to complete a daily online headache diary. Assessments to be captured are start/stop time, severity, associated symptoms, use of rescue medications, and unusual symptoms.
9. Administer Columbia-Suicide Severity Rating Scale (C-SSRS).
10. Schedule Visit 2.

VISIT 2 - RANDOMIZATION

1. Verify Inclusion/Exclusion Criteria. Subjects must continue to meet all inclusion (including ≥ 3 days of migraine during baseline) and none of the exclusion criteria.
2. Perform urine pregnancy test, if appropriate. Results of the pregnancy test must be negative to continue in study.
3. Measure vital signs (weight, resting heart rate, and blood pressure).
4. Record any changes to concomitant medications.
5. Record any Serious Adverse Events (SAE) since signing the Informed Consent.
6. Review Baseline Headache Diary for completeness and continuing eligibility.
7. Randomize subject
8. Review Month 1 Headache Diary instructions (same instructions as those discussed for Baseline Headache Diary).
9. Dispense Month 1 study medication. Subjects will be instructed how to take study medication, prohibited medications, dosage limitations of study medication, and storage requirements. Subjects will be instructed to return all used/partially

used/unused study medication at next office visit and medications reconciliation will be performed to ensure a compliance of at least 80%. Subjects not complying at an 80% level will be withdrawn, unless otherwise approved by the Sponsor and/or Clinvest. (Estimated to be < 10%)

10. Administer C-SSRS.
11. Administer MIDAS.
12. Collect serum samples for electrolytes, creatinine, and ionized Mg.
13. Schedule Visit 3.

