Table 1. Study Procedures

	Screening	Randomization	Treatment		
	Visit 1 Day 0	Visit 2 Day 29 (+/- 3)	Visit 3 Day 58 (+/- 3)	Visit 4 Day 87 (+/- 3)	Visit 5 Day 116 (+/- 3)
Informed Consent	X				
Physical/Neurological Exam	X				X
Vital Signs	X	X	X	X	X
Verify Inclusion/Exclusion	X	X			
Subject Randomization		X			
Medical History	X				
Migraine History	X				
Medication History	X				
Update Medications		X	X	X	X
Urine Pregnancy Test	X	X	X	X	X
SGIC					X
PGIC					X
Dispense Study Medication		X	X	X	
Drug Accountability			X	X	X
Headache Diary	X	X	X	X	
Review Diary		X	X	X	X
Collect Adverse Events		X	X	X	X
Administer C-SSRS	X	X	X	X	X
Administer MIDAS		X			X
Serum Electrolytes & Creatinine		X	X	X	X
Serum Ionized Mg		X	X	X	X

STUDY MEDICATION RANDOMIZATION

Eligible subjects will be randomized 1:1 to receive magnesium L-lactate dehydrate (243 mg of elemental mg⁺⁺ BID for a total of 486mg daily) or placebo at Visit 2. If at any time during the

study the subject withdrawals from the study, they will be instructed to return all used packaging and unused medication.

Group A

Subjects randomized to MLD10 (Group A) will be dispensed a 28 day supply of magnesium L-lactate dehydrate 10 mEq (121.5 mg of elemental mg⁺⁺ caplets) for daily treatment. A total of 120 caplets will be given each time at Visit 2, 3, and 4. Additional overage will be given to account for the 3 day window. Subjects will be instructed to take two caplets of study medication BID at about the same time each day (i.e. 8AM & 8PM for a total of 486mg's of elemental mg⁺⁺ per day). Subjects will be instructed regarding storage requirements and will be asked to return all used/partially used/unused medication containers at the next office visit.

Group B

Subjects randomized to placebo (Group B) will be dispensed a 28 day supply of matching placebo for daily treatment. A total of 120 caplets will be given each time at Visit 2, 3, and 4. Additional overage will be given to account for the 3 day window. Subjects will be instructed to take two caplets of study medication BID at about the same time each day (i.e. 8AM & 8PM). Subjects will be instructed regarding storage requirements and will be asked to return all used/partially used/unused medication containers at the next office visit.

RESCUE MEDICATION

Subjects will be instructed they may take their investigator approved rescue medications for headaches, if needed. Rescue medication usage and dosage will be recorded on the headache diary.

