At randomization (Visit 2), neither the subject nor the investigator will be aware to which treatment group the subject has been assigned. If needed, for safety and proper treatment of the subject, the investigator can unblind the subject's treatment assignment to determine which treatment has been assigned and institute appropriate follow-up care. When possible, Clinvest should be notified prior to unblinding study medication.

Individual unblinding envelopes are shipped with study medication. Each study medication kit has a corresponding unblinding envelope. Unblinding will include matching the kit and unblinding envelope with the subject drug number.

To unblind a subject without breaking the blind for remaining subjects' treatment the following instructions described below will be followed:

- Obtain the security envelope containing the unblinding envelopes.
- Remove the unblinding envelope with the study drug number corresponding with the study medication kit dispensed to the subject.
- Break the seal of the unblinding envelope and remove the subjects' treatment label.
- Return the subjects' treatment label to the unblinding envelope.
- Return the unblinding envelope to the security envelope.
- Document on the unblinding form located in the eAdmin Binder.
- Email copy of unblinding form to [contact] within 24 hours of unblinding.
- Complete and email or fax the Sterling IRB, unanticipated problem report form, to Sterling IRB within 10 business days of unblinding.

DISCONTINUATION/WITHDRAWAL FROM STUDY

All subjects who withdraw from the study, for any reason, must return all study medication and supplies to the investigator or his/her delegate at the first available opportunity.

Subjects may withdraw at any time or be dropped from the study at the discretion of the investigator or Clinvest if he/she violates the study plan or for administrative and/or safety reasons. When a subject discontinues/withdraws prior to study completion, all applicable activities scheduled for the final study visit should be performed at the time of discontinuation, as well as the completion of the early termination form and unscheduled visit form (if appropriate). Any adverse experiences which are present at the time of discontinuation/withdrawal should be followed in accordance with the safety requirements outlined in the adverse event reporting section of this protocol.

REPORTING PREGNANCY

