Non-Serious Adverse Event (NSAE)

NSAE's will be collected beginning after the first dose of study medication or within 14 days following cessation of treatment and will include any change from the subject's condition at Visit 2. These include physical findings, clinical signs and symptoms, or sequelae. Any worsening (i.e. any clinically significant adverse change in the frequency and/or intensity) of a preexisting condition which is temporally associated with the use of the provided product, is also considered to be an adverse event. Events such as medical/surgical procedures or anticipated day-to-day fluctuations of pre-existing conditions present at screening that do not worsen are not considered NSAE's.

All NSAE's noted will be captured on the non-serious adverse events eCRF. Information captured will include start date/time, end date/time, severity, relationship of causality to study drug, course of action taken, and outcome.

Serious Adverse Event (SAE)

An SAE is defined as any untoward medical occurring after signing of the informed consent and until cessation of the study which:

1. results in death.
2. is life threatening (Note: The term "life-threatening" in the definition of "serious" refers to an event in which the subject was at risk of death at the time of the event. It does not refer to an event, which hypothetically might have caused death, if it were more severe.).
3. requires subject hospitalization or prolongation of existing hospitalization.
4. results in persistent or significant disability/incapacity; or a congenital anomaly/birth defect.

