Medical or scientific judgment should be exercised in deciding whether reporting is appropriate in other situations, such as important medical events that may not be immediately life-threatening or result in death or hospitalization but may jeopardize the subject or may require medical or surgical intervention to prevent one of the other outcomes listed in the definition above. These should also be considered serious. SAE's will be reported in compliance with all applicable safety reporting requirements as set forth in the Code of Federal Regulations. SAE's assessed as life threatening or death "possibly related to the study medication" will be reported to Clinvest, Pharmalyte Solutions LLC, and Sterling IRB within 24 hours of knowledge of the event by study staff. All other SAE's (such as hospitalization, disability, congenital anomaly, and an important medical event) will be reported to Clinvest, Pharmalyte Solutions, and Sterling IRB within 48 hours of knowledge of the event by study staff. A MedWatch Form FDA 3500A will also be completed and forwarded to Pharmalyte Solutions LLC and Clinvest.

Included in the SAE Report Form will be an assessment of the causal relationship between the Pharmalyte Solutions LLC Materials and the SAE. SAE's will be followed

by study staff until the event(s) have returned to normal, stabilized, or have been otherwise explained, for at least 2 weeks following the last dose of study drug. If the investigator learns of any SAEs after a subject has been discharged from the study and he/she considers the event reasonably related to the investigational product, the investigator will notify Clinvest and Pharmalyte Solutions LLC.

CLINICAL SUPPLIES

Clinical supplies will be packaged for subjects in accordance to an allocation schedule generated by Clinvest.

LABORATORY ANALYSIS

Laboratory specimens for the serum ionized magnesium test will be shipped to the Center for Biomedical and Life Sciences for analysis. Laboratory specimens for the serum electrolytes and creatinine will be sent to the sites local laboratories for analysis. The collection, storage, shipping, and processing of the specimens will be documented.

STORAGE REQUIREMENTS

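### After the last dose the SAE rule does not match the 14-day rule for non-serious events: the end of SAE collection is undefined, and SAEs after discharge are notified only if judged related

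*Protocol*

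**What the plan says.** All of the text is in the Protocol.

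- **Serious Adverse Event (SAE), definition.** An SAE is "any untoward medical occurring after signing of the informed consent and until cessation of the study" that meets one of the listed seriousness criteria. The start is clear, and Visit 2 (Randomization) confirms it: "Record any Serious Adverse Events (SAE) since signing the Informed Consent". The end is not defined anywhere.
- **Non-Serious Adverse Event (NSAE).** "NSAE's will be collected beginning after the first dose of study medication or within 14 days following cessation of treatment". Relationship to study drug is a field recorded for each event, not a condition for recording it.
- **Serious Adverse Event (SAE), after discharge.** "If the investigator learns of any SAEs after a subject has been discharged from the study and he/she considers the event reasonably related" to the product, the contract research organization and the sponsor are notified. Nothing is said about SAEs in discharged subjects that are judged unrelated.
- **Serious Adverse Event (SAE), follow-up.** SAEs are followed until resolved, stable or explained, "for at least 2 weeks following the last dose of study drug".
- **Visit 5 and Table 1.** Visit 5 closes treatment month 3, and its last step is to exit the subject. No later visit or contact is scheduled.
- **Discontinuation/Withdrawal from Study.** For early leavers, "all applicable activities scheduled for the final study visit should be performed at the time of discontinuation".
- **Reporting Adverse Events.** Every adverse event is to be documented on the eCRF, related or not. An event seen after the first dose is treatment-emergent, and no end date is given.

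**The concern.** Treatment and participation end together, so the days just after the last dose are also the days just after discharge. In those days a mild non-serious event falls inside its collection window whatever its cause. A hospitalization judged unrelated has no clear route: either it is outside the SAE definition, or it is inside the definition but exempt from notification.

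At stake is the completeness and neutrality of early post-treatment safety data. Which SAEs are notified would depend on one investigator's opinion of causality, while non-serious events in the same days would not be selected in this way. Subjects who stop early are affected most in relative terms, because the tail is a larger share of their observation. Adverse-event comparison is a listed endpoint under Secondary Endpoints and Safety Endpoints. An analysis plan cannot recover reports that sites were never asked to send.

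**Working it through.** The plan states no figure on this point, so there is none to reproduce. The check compares the two windows by days and then sets the rules side by side under each meaning of the undefined end point.

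**Inputs**

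- Consent and screening: Day 0 (Table 1).
- First dose: about Day 29 (Table 1, "Visit 2 Day 29 (+/- 3" days).
- Last dose and exit: about Day 116 (Table 1, "Visit 5 Day 116 (+/- 3" days).
- Non-serious tail: 14 days after treatment ends. The NSAE sentence joins its two parts with an 'or'; I read it as running from first dose to 14 days after treatment.
- Assumption for the arithmetic: the SAE period ends at subject exit, and exit coincides with the last dose.

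**Formulas**

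- SAE window = exit day − 0.
- NSAE window = exit day + 14 − 29.
- Share of the NSAE window with no unconditional SAE cover = 14 / NSAE window.

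| Case | SAE window (days) | NSAE window (days) | Post-dose SAE / NSAE (days) | Share |
|---|---|---|---|---|
| Visit 5 on Day 116 | 116 | 116 + 14 − 29 = 101 | 0 / 14 | 14/101 = 13.9% |
| Visit 5 on Day 113 | 113 | 98 | 0 / 14 | 14/98 = 14.3% |
| Visit 5 on Day 119 | 119 | 104 | 0 / 14 | 14/104 = 13.5% |
| Leaves on Day 58 | 58 | 43 | 0 / 14 | 14/43 = 32.6% |
| Leaves on Day 43 (14 days of treatment) | 43 | 28 | 0 / 14 | 14/28 = 50% |

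In every row the SAE window is 15 days longer in total (29 days before the first dose minus the 14-day tail). Only the part after the last dose is shorter. The percentages are shares of days, not of events.

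**The two readings of the end point**

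1. *Subject exit.* An SAE that starts the day after Visit 5 is outside the definition. The post-discharge sentence brings it back only if it is judged related. A non-serious event on the same day is within its window regardless of cause.
2. *End of the whole trial.* The same SAE is within the definition. The SAE section then requires all SAEs other than possibly related deaths and life-threatening events to be reported within 48 hours, with no causality condition. The post-discharge sentence of the same section asks for notification only of related ones. It also sits badly with the rule under Reporting Adverse Events that relatedness does not decide documentation.

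The first reading leaves a gap and the second a contradiction. The two-week clause repairs neither: it governs how long identified SAEs are followed, not how long new ones are collected.

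**The case against.** The strongest reply has four parts.

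- **Serious events do not have the narrower window.** A reader might infer that they do, but the documents do not support it. SAE collection opens at consent, and on the subject-exit reading the total is 116 days against 101. This stands; the point is limited to the period after the last dose.
- **The gap in the definition depends on an assumption.** Elsewhere the protocol uses different words for a subject's end of treatment, discharge and exit, so the SAE end point may well mean the end of the trial. In that case the definition outlasts the 14 days for most subjects. This stands as far as the definition goes, but the relatedness condition after discharge then contradicts it, so the text is still not consistent.
- **Documentation is not notification.** A reader might infer that SAEs judged unrelated are lost from the safety data. The documents do not show that. The general rule requires every adverse event to be documented whatever its cause, and the post-discharge sentence speaks only of notification. This stands. What is shown is that such an SAE can go unnotified, and that sites have conflicting instructions.
- **The effect on the comparison is not shown.** The protocol plans no separate serious and non-serious comparison over matched risk periods, and no contact after Visit 5 gathers either kind of event. The 14-day difference on paper need not appear in the counts. This also stands, and it limits the size of the point without removing the inconsistency.

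**Conclusion.** The point holds in a limited form. After the last dose, non-serious events are collected for 14 days whatever their cause, while SAE collection ends at an undefined point and notification after discharge depends on judged relatedness. Neither reading of the end point gives sites one consistent rule.

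On the subject-exit reading the size is 14 days, about 14% of the non-serious window for a completer (13.5% to 14.3% across the Visit 5 allowance) and half of it for a subject who leaves after 14 days of treatment. These figures rest on exit coinciding with the last dose and on the NSAE sentence being read as a continuous window. On the end-of-trial reading no days are missing from the definition, and the problem is the conflicting notification rule.

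The protocol gives no expected SAE rate. With 71 subjects per arm and a two-week tail, few events are likely. The primary efficacy analysis and the power are unaffected. The text should still be changed, because the repair is small and the missing reports could not be recovered later.

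**What to change.** Reconcile four places in the Protocol: Visit 5, Reporting Adverse Events, Non-Serious Adverse Event (NSAE) and Serious Adverse Event (SAE).

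- State in the SAE definition that SAEs are collected and reported from informed consent until at least 14 days after the last dose, or until subject exit if that is later, regardless of causality. The 14 days are the tail the protocol already gives non-serious events. The words 'at least' and 'if later' make it a floor, so that the change does not shorten SAE collection if a longer period was intended.
- Apply the relatedness condition only to SAEs learned of after that window.
- Make clear that exit at Visit 5 or at early discontinuation does not end the duty to report SAEs within the window.
- Reword the NSAE sentence so that it reads as one continuous period.

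Scheduling a contact after Visit 5 is a separate question; a contact alone would not settle which SAEs must be notified.

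The cost is a short protocol change, matching SAE form instructions, and a few extra SAE reports. Sites already have a 14-day period to work to for non-serious events.
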